8.2. Key Secondary Efficacy Endpoints

There are six key secondary efficacy endpoints: CPA, Ishak histopathological stage, FibroScan[®], MBT, Brunt-Kleiner histopathological stage and complications of cirrhosis.

CPA

CPA will be used to measure liver collagen (a surrogate for fibrosis) by evaluation of liver biopsy at screening and 14 to 28 days after final dose (53 to 55 weeks). A single experienced pathologist, [name] (INNOVA Medical Center), will evaluate all liver biopsies at a central pathology laboratory.

The CPA will be summarized for the FAS population by visit and treatment group, for all scheduled visits, along with the change from baseline descriptively in a summary table and graphically.

Ishak histopathological stage

Fibrosis will be evaluated by liver biopsy and be staged according to the Ishak histopathological stage (0-6) at screening and 14 to 28 days after final dose (53 to 55 weeks). The number and percentage of subjects by Ishak histopathological stage will be summarized using the FAS population by treatment group. The number and percentage of subjects changing in Ishak histopathological stages will also be presented.

FibroScan[®]

FibroScan[®] will be only performed at the study centers where it is available and used to evaluate liver stiffness which is recorded as the pressure measurement of kPa at the scheduled visits.

The FibroScan[®] (if available) will be summarized for the FAS population by visit and treatment group, for all scheduled visits, along with the change from baseline descriptively in a summary table and graphically.

MBT

The MBT will only be performed at the study centers where it is approved. The cumulative percentage dose recovery of the metabolized ¹³C-methacetin 30 minutes after ingestion of the test substrate will be used as the MBT parameter for this study. Delta over baseline (DOB) with corresponding time point (T_n) will be collected on the eCRF.

The $cPDR_{30}$ is defined as:

$$cPDR_{30} = \frac{\frac{T_1}{60} \cdot PDR_1}{2} + \sum_{i=2}^n \frac{\frac{T_i - T_{i-1}}{60} \cdot (PDR_i + PDR_{i-1})}{2}$$

where $PDR_i = 1.817853 \times DOB_i \times w^{0.5378} \times h^{0.3963}$, $w = weight$ (kg), $h = height$ (cm).

Brunt-Kleiner histopathological stage

Fibrosis will be evaluated by liver biopsy and be staged according to the Brunt-Kleiner histopathological stage (0-4) at screening and 14 to 28 days after final dose (53 to 55 weeks).

The number and percentage of subjects by Brunt-Kleiner histopathological stage will be summarized using the FAS population by treatment group. The number and percentage of subjects changing in Brunt-Kleiner histopathological stages will also be presented.

Complications of cirrhosis

Complications of cirrhosis with portal hypertension is defined as the development of any of the following:

- esophageal variceal hemorrhage or portal hypertensive gastropathy hemorrhage (confirmed by endoscopy or interventional radiology)
- clinically apparent ascites
- spontaneous bacterial peritonitis
- overt hepatic encephalopathy
- an increase in Child-Turcotte-Pugh Score ≥ 2 points
- newly diagnosed varices in a subject without prior varices
- progression from small to medium or large varices
- qualification for liver transplant defined as a MELD score ≥ 15
- listing for a liver transplant or the performance of a liver transplant
- liver-related mortality

The incidence of complications will be summarized in a table with count and percentage of subjects by each complication event using the FAS population by treatment group. Subjects with any complication event will also be presented.

In addition, Child-Turcotte-Pugh score and MELD score will be summarized descriptively at the scheduled visits. Child-Turcotte-Pugh class and MELD score (<15 , ≥ 15) will also be summarized.

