#### **4.1.2 Exclusion Criteria**

Subjects meeting any of the following criteria will be excluded from the study:

1. Has a history of hepatic decompensation including any episode of variceal bleeding, clinically detectable ascites, or overt hepatic encephalopathy (defined by the clinical judgment of the principal investigator but should include the presence of lethargy, disorientation, inappropriate behavior, and the presence of asterixis).

2. Has a presence of medium or large varices or varices with red signs regardless of size based on endoscopy.
  - Small varices are defined by veins that occupy >25% of the distal one third of the esophageal lumen when insufflated. Veins that completely flatten upon insufflation of the esophagus are not considered varices. Any varices larger than that are medium (up to 50%) or large (>50%).
  - Red signs include red wale markings (dilated venules oriented longitudinally on the variceal surface), cherry red spots (small, red, spotty dilated venules usually approximately 2 mm in diameter on the variceal surface) or hematocystic spots (large, round, crimson red projection >3 mm that look like a blood blister on the variceal surface).
3. Has had a prior transjugular porto-systemic shunt procedure.
4. Has evidence of other forms of chronic liver disease including viral hepatitis B or C, primary biliary cirrhosis, primary sclerosing cholangitis, Wilson's disease, alpha-1 antitrypsin deficiency, alcoholic hepatitis, hemochromatosis, liver cancer, history of biliary diversion, or autoimmune hepatitis.
5. Has any of the following laboratory values:
  - a. Serum alanine aminotransferase levels  $>10 \times$  the upper limits of normal
  - b. Serum aspartate aminotransferase levels  $>10 \times$  the upper limits of normal
  - c. Serum creatinine  $\geq 2.0$  mg/dL
  - d. Platelet count  $<60\,000/\text{mm}^3$
  - e. Serum albumin  $\leq 2.8$  g/dL
  - f. International normalized ratio (INR)  $\geq 1.7$
  - g. Direct bilirubin  $\geq 2.0$  mg/dL
6. A MELD score  $\geq 15$  or Child-Turcotte-Pugh Class B or C.

7. Is unwilling or unable to safely undergo HVPG or liver biopsy.
8. Has known positivity for human immunodeficiency virus (HIV) infection or a positive HIV test result at screening.
9. Has had major surgery within 8 weeks of randomization, significant traumatic injury within 6 months, or anticipation of need for major surgical procedure during the course of the study.

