### **7.3 Exploratory Endpoints**

Exploratory endpoints are to evaluate:

- Difference in health-related quality of life (using the subject-completed CLDQ) following administration of GR-MD-02 or placebo at 1 year
- Baseline-adjusted change in FibroTest (FibroSure) and ELF score at Infusion Visits 7, 13, 20, and 14-28 days after final infusion
- Changes in liver biopsy staining for alpha smooth muscle and galectin-3 in subjects treated with GR-MD-02 or placebo at 1 year
  - HVPG  $\geq 10$  and  $< 15$  mm Hg (elevated portal pressure, with potential development of varices, classified as clinically significant portal hypertension)
  - HVPG  $\geq 15$  (increased incidence of complications from varices)

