4.2. Randomization, Stratification, and Blinding

Approximately 156 eligible subjects will be randomly assigned to one of the following 3 treatment groups in a 1:1:1 ratio:

- Approximately 52 subjects are assigned to GR-MD-02 in dose of 2 mg/kg LBM
- Approximately 52 subjects are assigned to GR-MD-02 in dose of 8 mg/kg LBM
- Approximately 52 subjects are assigned to placebo

The randomization mechanism for the study will be deployed within an interactive web response system (IWRS). Unblinded biostatisticians will generate the randomization schedule using SAS software Version 9.2 or later for IWRS which will link sequential subject randomization numbers to treatment codes allocated at random with a 1:1:1 randomization ratio.

Except in an emergency, investigators, Galectin, or other persons involved in study conduct will not know the randomization schedule and study drug allocation before study completion. The IWRS system will be used if emergency unblinding is required. This would generally only be used in an emergency, when knowledge of the actual treatment becomes medically necessary.

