4.3. Analysis Set

4.3.1. Full-Analysis Set

The full-analysis set (FAS), or intent-to-treat group, will consist of all subjects who were randomly assigned to IMP. The FAS will be used as the primary efficacy analysis set.

All subjects in the FAS set will be analyzed according to the treatment they were randomized to receive.

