- Change from baseline in FibroScan[®] (if available) at 1 year will be analyzed using the MITT population.
- Change from baseline in FibroScan[®] (if available) at 1 year will be analyzed using the PP population.
- Treatment effect for FibroScan[®] (if available) overtime will be estimated using a mixed model repeated measures (MMRM) analysis with the FAS population.

MBT

The change from baseline in MBT (if available) at 1 year will be analogous to the primary efficacy endpoint, using the ANCOVA model using the FAS population. The baseline MBT will be used as a continuous covariate in the ANCOVA model.

Sensitivity analyses for MBT (if available) will include:

- Change from baseline in MBT (if available) at 1 year will be analyzed based on the LOCF values using the FAS population.
- Change from baseline in MBT (if available) at 1 year will be analyzed using the MITT population.
- Change from baseline in MBT (if available) at 1 year will be analyzed using the PP population.
- Treatment effect for MBT (if available) overtime will be estimated using MMRM analysis with the FAS population.

Brunt-Kleiner histopathological stage

The proportion of subjects who have at least one stage change in Brunt-Kleiner histopathological staging of fibrosis at 1 year will be analyzed using the FAS population. Fisher Exact Test will be used to compare the difference between treatment groups.

Sensitivity analyses for Brunt-Kleiner histopathological stage will include:

- The proportion of subjects who have at least one stage change in Brunt-Kleiner histopathological staging of fibrosis at 1 year will be analyzed using the MITT population.
- The proportion of subjects who have at least one stage change in Brunt-Kleiner histopathological staging of fibrosis at 1 year will be analyzed using the PP population.

Complications of cirrhosis

The incidence of complications of cirrhosis with portal hypertension at 1 year will be analyzed using the FAS population. A standard chi-square test will be used to compare the incidence of complications of cirrhosis between treatment groups.

Sensitivity analyses for complications of cirrhosis will include:

- The incidence of complications of cirrhosis with portal hypertension at 1 year will be analyzed using the MITT population.
- The incidence of complications of cirrhosis with portal hypertension at 1 year will be analyzed using the PP population.

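### Two varices rows of the complications table use the whole FAS as denominator, and the composite test leaves out baseline HVPG

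*SAP*

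**What the plan says.** SAP section 8.2 (Complications of cirrhosis) lists ten events and has their incidence "summarized in a table with count and percentage of subjects by each complication event using the FAS population by treatment group". Under SAP section 4.3.1 the FAS "will consist of all subjects who were randomly assigned to IMP. The FAS will be used as the primary efficacy analysis set".

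Two of the ten events are conditional on baseline status: "newly diagnosed varices in a subject without prior varices" and "progression from small to medium or large varices". Protocol section 4.1.2 excludes a subject who "Has a presence of medium or large varices or varices with red signs regardless of size based on endoscopy", so an eligible subject enters with either no varices or small ones.

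For the comparison, SAP section 8.2.1 states: "A standard chi-square test will be used to compare the incidence of complications of cirrhosis between treatment groups". The analysis is repeated on the MITT and PP sets. A Kaplan-Meier and log-rank sensitivity analysis follows, with no strata or covariates named. By contrast, the HVPG, FibroScan and MBT analyses all carry the baseline value as a covariate.

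Protocol section 7.3 describes HVPG from 10 to below 15 mm Hg as "elevated portal pressure, with potential development of varices, classified as clinically significant portal hypertension", and associates 15 mm Hg or more with more complications from varices. SAP section 8.1 already defines two HVPG classes, below 10 and 10 mm Hg or more. SAP section 4.2 describes "treatment codes allocated at random with a 1:1:1 randomization ratio" and names no stratification factor. Baseline varices status is not among the disease characteristics named in SAP section 6.2, although that list is not exhaustive.

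**The concern.** A percentage is readable when its denominator holds the subjects who could have had the event. For the two varices rows it does not. A subject with small varices at entry cannot develop new varices, and a subject with none cannot progress from small. Each row therefore mixes the incidence among those at risk with the share of the arm at risk, and two arms can print different percentages with no drug effect.

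Both events are also found mainly by the endoscopy 14 to 28 days after the last dose. SAP section 4 imputes nothing unless specified, and no rule classifies a subject without that examination. On a FAS denominator such a subject is in effect counted as free of the event.

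The second issue is the composite test. Baseline HVPG is measured in every subject and is, on the protocol's own account, prognostic for varices and their complications. Leaving it out gives up some precision, and an unlucky allocation stays in the estimate. This is the trial's composite of clinical events, so a clear reading is worth having.

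**Working it through.** **1. The plan's own figure.** The only sample size in the documents is for HVPG change: difference 2 mm Hg, SD 3 mm Hg, two-sided 0.05, 80% power. The normal formula gives 2 × (1.96 + 0.84)² × 3² / 2² = 35.3, so 36 per arm. The exact t-test gives 37. Dividing by 0.75 for 25% dropout gives 49.3, so 50 against the stated 52, which is close and slightly conservative. No event rate, varices share or power is stated for complications, so the rates below are assumptions.

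**2. Dilution of the two rows.** Printed percentage = incidence among those at risk × share at risk. Assume 20% incidence in each at-risk group and let q be the share without varices at baseline.

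| q | Without varices, of 52 | New varices, % of FAS | Progression, % of FAS |
|---|---|---|---|
| 0.3 | 15.6 | 6 | 14 |
| 0.5 | 26.0 | 10 | 10 |
| 0.7 | 36.4 | 14 | 6 |

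**3. Dependence on the arm's mix.** Suppose 20% at-risk incidence in both arms and no drug effect.
- With q of 55% and 45%, the new-varices row prints 11% and 9%. With 60% and 40% it prints 12% and 8%.
- With 52 per arm and no stratification, the exact binomial chance that two arms differ by at least 10 points in q is 24 to 28% for q between 0.3 and 0.7. For at least 15 points it is 11 to 14%.
- The 60/40 case is rarer. At q = 0.5 the SD of the difference is √(2 × 0.5 × 0.5 / 52) = 0.098, so 20 points is 2.04 SDs, about 4% two-sided.

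**4. HVPG mix.** In the placebo data quoted in Protocol section 7.6, 50 of 82 subjects (61%) had HVPG of 10 mm Hg or more. At that share, two arms of 52 differ by at least 10 points with probability 27%, and by at least 15 points with probability about 13%.

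**5. Chi-square against a test stratified by HVPG class.** Simulation with 20,000 trials per setting, one active arm against placebo, 52 per arm, 61% at 10 mm Hg or more. Placebo risks are assumed in each class, with a common odds ratio (OR).

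| Placebo risk, <10 / ≥10 mm Hg | OR | Chi-square | Stratified |
|---|---|---|---|
| 5% / 25% | 0.4 | 29.1% | 30.7% |
| 5% / 25% | 0.25 | 50.7% | 52.2% |
| 10% / 40% | 0.4 | 41.0% | 43.1% |
| 10% / 40% | 0.25 | 68.8% | 71.8% |
| 5% / 40% | 0.4 | 36.9% | 40.7% |
| 5% / 40% | 0.25 | 64.3% | 68.7% |

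The gain is 1.5 to 4.4 points of power.

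Under no effect (OR 1), type I error over all trials is 4.8 to 5.4% for the chi-square and 4.9 to 5.2% for the stratified test. In the roughly 13% of trials with an HVPG imbalance of at least 15 points it is 7.7 to 10.5% for the chi-square and 4.9 to 5.3% for the stratified test.

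**6. Size of the shift in one trial.** With assumed risks of 30% and 4%, a 15-point imbalance moves the risk difference by 0.15 × (0.30 − 0.04) = 3.9 points. Overall risk is 0.61 × 0.30 + 0.39 × 0.04 = 0.199, so the standard error of the difference is √(2 × 0.199 × 0.801 / 52) = 7.8 points. The shift is half a standard error.

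**The case against.** The strongest defence is that the tested quantity is the composite and nothing is wrong with its test. Every eligible subject is at risk of exactly one of the two varices events and of the remaining components, so the FAS is the proper denominator. The chi-square is the protocol's prespecified method and holds its size over all trials (step 5). The shift in step 6 is sampling variation that the test already allows for. All of this stands, and it confines the denominator issue to two rows of a descriptive table.

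Some provisions also help in part. The log-rank analysis censors event-free subjects at their last complications assessment. The 26 January 2018 SAP addendum (item 5) tests each separate complication in subjects without baseline varices, which is the at-risk set for new varices. But the addendum is post hoc, has no counterpart for complications in subjects with small varices, and is also unadjusted.

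On missing endoscopies, a reader might combine a 50% share at risk with the 25% planned dropout and infer that a 20% incidence prints as 0.20 × 0.5 × 0.75 = 7.5%. That requires every dropout to lack a final endoscopy. Protocol section 4.2.2 seeks all end-of-study assessments in early terminators where possible, and SAP section 3.1 does so after at least 13 infusions. The 7.5% is therefore an extreme case.

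It is also fair that analysing only subjects with a final endoscopy would condition on something that happens after randomization, and informative dropout could bias that comparison.

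**Conclusion.** The point holds as an improvement to reporting and precision. The two varices rows are diluted by construction. The size depends on the unstated varices share: 6 to 14% printed for a 20% at-risk incidence, for shares of 30 to 70%. The unadjusted composite test gives up about 2 to 4 points of power under the assumed rates and offers no protection in the roughly one trial in eight with a large HVPG imbalance.

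Three stronger readings are not supported:
- A reader might infer that the chi-square is biased or that the FAS is wrong for the composite. Neither is so.
- A reader might infer that the documents show overall risk to depend on baseline varices. They tie risk to HVPG. For varices they give only the event definitions and no rates by status.
- A reader might infer that randomization must be stratified. The stratified test does not need it, and the addendum already speaks of a randomized subject, so new strata would come too late.

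Severity is minor to moderate. The endpoint is sixth of six in the gatekeeping order and is tested formally only if the primary and five earlier secondary endpoints succeed.

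**What to change.** **SAP 8.2.** Keep the FAS percentage for the composite and for every row. Beside it, give new varices per subject without varices at baseline and progression per subject with small varices at baseline. For each of these two groups show by arm how many had a final endoscopy and how many were not examined, instead of restricting the rows to those examined.

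**SAP 8.2.1.** Replace the chi-square, for each dose against placebo, by a Cochran-Mantel-Haenszel test and a common risk difference stratified by baseline HVPG class (below 10, 10 mm Hg or more). Add baseline varices (none, small) as a second factor only if the strata are not sparse, and state the collapsing rule in advance.

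**Cost.** SAP wording and table shells only. HVPG class and baseline endoscopy are already collected. The downside is that with 52 per arm and possibly few events, four strata may have to be collapsed to HVPG class alone.

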8.2.1. Key Secondary Efficacy Analysis

The 6 key secondary efficacy endpoints will be examined using a gatekeeper statistical approach and will be tested sequentially in the order of 1) CPA, 2) FibroScan[®], 3) Ishak histopathological stage, 4) MBT, 5) Brunt-Kleiner histopathological stage, 6) complications of cirrhosis. Analysis of the secondary endpoints will be conducted if the primary endpoint is significant ($\alpha < 0.05$). If a secondary endpoint does not meet statistical significance, then all the subsequent secondary endpoints will be treated as exploratory.

CPA

The change from baseline in CPA at 1 year (53 to 55 weeks), will be analyzed using robust regression (M estimation method, Huber 1973) using the FAS population at a significant level of 0.05 (2-sided). Treatment effect will be evaluated as a contrast of each active treatment versus placebo and described using continuous summary.

Sensitivity analyses for CPA will include:

- Change from baseline in CPA at 1 year will be analyzed based on the LOCF values using the FAS population.
- Change from baseline in CPA at 1 year will be analyzed using the MITT population.
- Change from baseline in CPA at 1 year will be analyzed using the PP population.

Ishak histopathological stage

The proportion of subjects who have at least one stage change in Ishak histopathological staging of fibrosis at 1 year will be analyzed using the FAS population. Fisher Exact Test will be used to compare the difference between treatment groups.

Sensitivity analyses for Ishak histopathological stage will include:

- The proportion of subjects who have at least one stage change in Ishak histopathological staging of fibrosis at 1 year will be analyzed using the MITT population.
- The proportion of subjects who have at least one stage change in Ishak histopathological staging of fibrosis at 1 year will be analyzed using the PP population.

FibroScan[®]

The change from baseline in FibroScan[®] (if available) at 1 year will be analogous to the primary efficacy endpoint, using the ANCOVA model for the FAS population. The baseline value of FibroScan[®] (if available) will be used as a continuous covariate in the ANCOVA model.

Sensitivity analyses for FibroScan[®] (if available) will include:

- Change from baseline in FibroScan[®] (if available) at 1 year will be analyzed based on the LOCF values using the FAS population.
- Change from baseline in FibroScan[®] (if available) at 1 year will be analyzed using the MITT population.
- Change from baseline in FibroScan[®] (if available) at 1 year will be analyzed using the PP population.
- Treatment effect for FibroScan[®] (if available) overtime will be estimated using a mixed model repeated measures (MMRM) analysis with the FAS population.

MBT

The change from baseline in MBT (if available) at 1 year will be analogous to the primary efficacy endpoint, using the ANCOVA model using the FAS population. The baseline MBT will be used as a continuous covariate in the ANCOVA model.

Sensitivity analyses for MBT (if available) will include:

- Change from baseline in MBT (if available) at 1 year will be analyzed based on the LOCF values using the FAS population.
- Change from baseline in MBT (if available) at 1 year will be analyzed using the MITT population.
- Change from baseline in MBT (if available) at 1 year will be analyzed using the PP population.
- Treatment effect for MBT (if available) overtime will be estimated using MMRM analysis with the FAS population.

Brunt-Kleiner histopathological stage

The proportion of subjects who have at least one stage change in Brunt-Kleiner histopathological staging of fibrosis at 1 year will be analyzed using the FAS population. Fisher Exact Test will be used to compare the difference between treatment groups.

Sensitivity analyses for Brunt-Kleiner histopathological stage will include:

- The proportion of subjects who have at least one stage change in Brunt-Kleiner histopathological staging of fibrosis at 1 year will be analyzed using the MITT population.
- The proportion of subjects who have at least one stage change in Brunt-Kleiner histopathological staging of fibrosis at 1 year will be analyzed using the PP population.

Complications of cirrhosis

The incidence of complications of cirrhosis with portal hypertension at 1 year will be analyzed using the FAS population. A standard chi-square test will be used to compare the incidence of complications of cirrhosis between treatment groups.

Sensitivity analyses for complications of cirrhosis will include:

- The incidence of complications of cirrhosis with portal hypertension at 1 year will be analyzed using the MITT population.
- The incidence of complications of cirrhosis with portal hypertension at 1 year will be analyzed using the PP population.
- Time to complications of cirrhosis will be analyzed using Kaplan-Meier curves and compared between treatment groups using a log-rank test. Median time to

complications of cirrhosis, Q1 and Q3 will be presented, along with 95% CI. Time to complications of cirrhosis is defined as the time from the date of randomization to the first documentation of any complication of cirrhosis described in section 8.2. Subjects without development of complications of cirrhosis will be censored at the date of last assessment of cirrhosis complications.

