### 7.2 Secondary Efficacy Endpoints

The secondary endpoints are:

- The baseline-adjusted absolute change in the CPA at 1 year as determined by digital morphometric analysis of liver biopsies
- The baseline-adjusted change in liver stiffness as determined by FibroScan score prior to the first infusion, at Infusion Visit 13, and 14-28 days after final infusion
- The baseline-adjusted change in the metabolic capacity of the liver as determined by cPDR30 of the MBT (if available) at screening, Infusion Visit 13, and 14-28 days after final infusion
- The difference between GR-MD-02-treated and placebo-treated subjects in the progression of cirrhosis at 1 year, defined as the development of any of the following:
  - esophageal variceal hemorrhage or portal hypertensive gastropathy hemorrhage (confirmed by endoscopy or interventional radiology)
  - clinically apparent ascites
  - spontaneous bacterial peritonitis
  - overt hepatic encephalopathy

- an increase in Child-Turcotte-Pugh score  $\geq 2$
- newly diagnosed varices in a subject without prior varices
- progression from small to medium or large varices
- qualification for liver transplant defined as a MELD score  $\geq 15$
- listing for a liver transplant or the performance of a liver transplant
- liver-related mortality

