### **7.9.2 Analysis of Key Secondary Efficacy Endpoints**

Key secondary endpoints will be examined using a gatekeeper statistical approach. If the primary endpoint is significant ( $\alpha < 0.05$ ), analysis will proceed to the secondary endpoints. Since the evaluation of secondary endpoints will proceed using a prespecified hierarchy without statistical correction for multiplicity, if a secondary endpoint does not meet statistical

significance, all subsequent analysis will be treated as exploratory only. The key secondary endpoints will be evaluated in the following sequence:

- Baseline-adjusted mean change in CPA will be compared between treatment groups using robust regression (M estimation method, [Huber 1973](#)) to account for skewedness of the data with adjustment for baseline CPA.
- The baseline-adjusted mean change in FibroScan at 1 year will be analyzed using similar methods previously defined for the primary efficacy endpoint
- The baseline-adjusted mean change in MBT (if available) at 1 year will be analyzed using similar methods previously defined for the primary efficacy endpoint
- The incidence of complications of cirrhosis with portal hypertension at 1 year will be compared between groups using chi-square analysis.

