3.2.2. Secondary Endpoints

- The baseline-adjusted mean change in the CPA at 1 year as determined by digital morphometric analysis of liver biopsies
- Proportion of subjects who have at least one stage change in Ishak histopathological staging of fibrosis at 1 year as assessed on liver biopsy
- The baseline-adjusted mean change in liver stiffness as determined by FibroScan[®] (if available) score prior to the first infusion, at Infusion Visit 13, and 14 to 28 days after final infusion
- The baseline-adjusted mean change in the metabolic capacity of the liver as determined by cPDR₃₀ of the MBT (if available) at screening, Infusion Visit 13, and 14 to 28 days after final infusion
- Proportion of subjects who have at least one stage change in Brunt-Kleiner histopathological staging of fibrosis at 1 year as assessed on liver biopsy

- The difference between GR-MD-02-treated and placebo-treated subjects in the progression of cirrhosis at 1 year, defined as the development of any of the following:
 - esophageal variceal hemorrhage or portal hypertensive gastropathy hemorrhage (confirmed by endoscopy or interventional radiology)
 - clinically apparent ascites
 - spontaneous bacterial peritonitis
 - overt hepatic encephalopathy
 - an increase from baseline in Child-Turcotte-Pugh Score ≥ 2 points
 - newly diagnosed varices in a subject without prior varices
 - progression from small to medium or large varices
 - qualification for liver transplant defined as a MELD score ≥ 15
 - listing for a liver transplant or the performance of a liver transplant
 - liver-related mortality

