 - b. Percent Change from BL HVPG vs dose with no covariate/no baseline adjustment
3. Perform similar ANCOVA/ANOVA analyses of MPH and CSPH for each subset, this would result in the following:
 - a. Analyses of patients without varices and with MPH – using FAS LOCF, mITT LOCF and PP LOCF for HVPG with LSD mean comparison (no Bonferroni correction) on:
 - i. ANCOVA for BL Change in HVPG vs dose with BL HVPG as a covariate (i.e. adjust for baseline HVPG)
 - ii. ANOVA for Percent Change from BL HVPG vs dose with no covariate/no baseline adjustment
 - b. Analyses of patients without varices and with CSPH - using ITT LOCF, mITT LOCF, and PP LOCF for HVPG with LSD mean comparison (no Bonferroni correction) on:
 - i. ANCOVA for BL Change in HVPG vs dose with BL HVPG as a covariate (i.e. adjust for baseline HVPG)
 - ii. ANOVA for Percent Change from BL HVPG vs dose with no covariate/no baseline adjustment

- c. Analyses of patients with varices and with MPH (6 to <10 mmHg) -- using ITT LOCF, mITT LOCF and PP LOCF for HVPG with LSD mean comparison (no Bonferroni correction) on:
 - i. ANCOVA for BL Change in HVPG vs dose with BL HVPG as a covariate (i.e. adjust for baseline HVPG)
 - ii. ANOVA for Percent Change from BL HVPG vs dose with no covariate/no baseline adjustment
- d. Analyses of patients with varices and CSPH (≥ 10 mmHg) -- using ITT LOCF, mITT LOCF, and PP LOCF for HVPG with LSD mean comparison (no Bonferroni correction) on:
 - i. ANCOVA for BL Change in HVPG vs dose with BL HVPG as a covariate (i.e. adjust for baseline HVPG)
 - ii. ANOVA for Percent Change from BL HVPG vs dose with no covariate/no baseline adjustment

Analyses on Secondary Endpoint Collagen Proportional Area (CPA)

All post-hoc analysis performed on HVPG parameter will be repeated for Collagen Proportional Area (CPA).

Analyses on Secondary Endpoints using FAS set

1. Perform BL Change vs. Dose using MMRM model for continuous data and Ordinal Logistic Regression (OLR) Analysis for categorical data for the following datasets: all data, With Varices, Without Varices, Without Varices and MPH, Without Varices and CSPH, With Varices and MPH, and With Varices and CSPH.

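### The SAP's CPA model paragraph omits the baseline-CPA covariate that the SAP's own endpoint definition and the protocol call for; run as written, the first gated secondary is tested less precisely

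*SAP*

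**What the plan says.** The documents describe the CPA analysis in four places.

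- Protocol 7.2 defines the endpoint: "The baseline-adjusted absolute change in the CPA at 1 year as determined by digital morphometric analysis of liver biopsies".
- Protocol 7.9.2 chooses robust regression by M-estimation "to account for skewedness of the data with adjustment for baseline CPA".
- SAP 3.2.2 keeps the adjustment in its definition: "The baseline-adjusted mean change in the CPA at 1 year as determined by digital morphometric analysis of liver biopsies".
- SAP 8.2.1, the paragraph a programmer would work from, says that the change "will be analyzed using robust regression (M estimation method, Huber 1973) using the FAS population at a significant level of 0.05 (2-sided". It adds contrasts of each active dose with placebo and names no covariate. The LOCF, MITT and PP repeats listed below it name none either.

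The other continuous endpoints are treated differently. SAP 8.1.1 takes baseline HVPG as a covariate. In SAP 8.2.1 the FibroScan baseline "will be used as a continuous covariate in the ANCOVA model", and for the breath test "The baseline MBT will be used as a continuous covariate in the ANCOVA model". Both of these are also declared analogous to the primary analysis. The CPA paragraph has no such cross-reference, so it inherits nothing.

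CPA leads the hierarchy. The secondaries "will be tested sequentially in the order of 1) CPA, 2) FibroScan", followed by four more, and a failure makes all later ones exploratory.

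**The concern.** A change score is not baseline adjustment. Follow-up values regress towards the mean, so the change stays negatively correlated with baseline. Leaving baseline out of the model has two effects: the residual variance is larger than it needs to be, and any chance baseline difference between arms passes partly into the treatment contrast.

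CPA's position in the hierarchy makes this matter. If HVPG succeeds, CPA decides whether the other five secondaries can be tested formally. The two readings of the plan, with and without baseline CPA, give different estimates and p-values, so the choice should be fixed before the data are unblinded.

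**Working it through.** **The plan's own figure.** The only sample-size figure is for HVPG (protocol 7.6): difference 2 mm Hg, SD 3 mm Hg, two-sided α 0.05, power 80%, two-sample t-test, 25% dropout. This needs 37 completers per arm, and 37/0.75 = 49.3, so 50 randomized against the stated 52. The figure reproduces to within 2 subjects per arm. It does not depend on the CPA model, and none is given for CPA. I use it only for the number of completers: 52 × 0.75 = 39 per arm.

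**Variance.** Let baseline and 1-year CPA have equal SD s and correlation r (assumptions).

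- Unadjusted change: variance 2s²(1 − r).
- Change adjusted for baseline: variance s²(1 − r²).
- Adjusted/unadjusted ratio: (1 − r²)/[2(1 − r)] = (1 + r)/2.
- Unadjusted standard error relative to adjusted: 1/√[(1 + r)/2].
- Power of the unadjusted test when the adjusted test has 80%: Φ(2.80·√[(1 + r)/2] − 1.96).

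These are least-squares results. I checked them for Huber M-estimation by simulation: three arms of 39, 1,500 trials per setting, with normal data and with right-skewed data. The skewed values are exponentials of half a normal variable, and r refers to the underlying normal scale.

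| r (assumed) | (1 + r)/2 | Simulated ratio, normal / skewed | Unadjusted SE larger by | Unadjusted power |
|---|---|---|---|---|
| 0.3 | 0.65 | 0.66 / 0.61 | 24% | 62% |
| 0.5 | 0.75 | 0.76 / 0.65 | 15% | 68% |
| 0.7 | 0.85 | 0.84 / 0.83 | 8% | 73% |
| 0.9 | 0.95 | 0.94 / 0.93 | 3% | 78% |

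**The one correlation the documents allow.** Protocol Tables 7-1 and 7-2 give placebo HVPG SDs of 3.97 (baseline), 3.82 (12 months) and 2.85 (change):

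- r = (3.97² + 3.82² − 2.85²)/(2 × 3.97 × 3.82) = 22.23/30.33 = 0.73.
- Adjusted residual SD = 3.82 × √(1 − 0.73²) = 2.60.
- 2.85/2.60 = 1.10, so the unadjusted standard error is about 10% larger.

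This is HVPG, not CPA, and serves as an illustration only.

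**Chance imbalance.** Given a baseline difference D between two arms, the unadjusted contrast is shifted by (r − 1)D. With 39 per arm, one standard error of D is √(2/39) = 0.23 SD. A difference of that size shifts the contrast by 0.16 SD at r = 0.3, 0.11 SD at r = 0.5, 0.07 SD at r = 0.7 and 0.02 SD at r = 0.9, in the direction opposite to D.

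**The case against.** The strongest reply is that this is a gap in wording, not a decision. A reader might infer that the SAP deliberately moved to an unadjusted CPA model. The documents do not support that: no text removes the adjustment or gives a reason, and SAP 3.2.2 still calls the endpoint baseline-adjusted. The SAP Addendum leans the same way. It says "All post-hoc analysis performed on HVPG parameter will be repeated for Collagen Proportional Area (CPA", and those HVPG analyses include change models with baseline as covariate. This stands, and it makes the loss of precision conditional on 8.2.1 being followed literally. It does not repair 8.2.1. The addendum analyses are post hoc, are ANCOVA and ANOVA rather than robust regression, and include percent-change models without baseline.

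Second, the protocol supplied is the original of 20 February 2015. The SAP differs from it elsewhere, for example in requiring Ishak stage 5 or 6 only and in adding histology endpoints. A later protocol text may have changed the CPA model. This limits what can be said about a conflict with the protocol. The conflict between SAP 3.2.2 and SAP 8.2.1 does not depend on it.

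Third, the harm is limited. A reader might infer that the unadjusted test is biased or has an inflated type I error. Neither follows: over randomization the contrast is unbiased and the error rate holds. The imbalance effect is conditional on the sample drawn, and the endpoint is formally tested only if HVPG succeeds.

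Fourth, the upper end of the loss needs r = 0.3, which no document supports. That is why the range runs to r = 0.9 and the HVPG value is shown.

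**Conclusion.** The point holds as an internal inconsistency of the SAP, supported by the protocol text available: 8.2.1 gives treatment contrasts only, where 3.2.2 and protocol 7.9.2 call for baseline adjustment. CPA is the only continuous key secondary whose model names no baseline covariate.

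The size of the loss, if 8.2.1 is run as written, cannot be fixed from the documents. It is about 3% to 24% in standard error for assumed r of 0.9 to 0.3, under equal SDs, and about 10% if CPA behaves as HVPG did in the cited placebo data. The cost is precision and exposure to chance imbalance, not validity.

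A reader might extend the point to α-SMA and galectin-3 staining in SAP 8.3, which also use robust regression. The documents do not clearly support that. The opening of 8.3 already calls for the baseline value of each exploratory endpoint as a covariate, although it refers to the ANCOVA model and so is ambiguous for robust regression.

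**What to change.** In SAP 8.2.1, state that change from baseline in CPA at 1 year is analysed by M-estimation robust regression with treatment group (two indicators, placebo as reference) and baseline CPA as a continuous covariate. State that the LOCF, MITT and PP repeats use the same model. If the adjustment was in fact meant to be removed, record the reason and amend 3.2.2 to match.

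The cost is one sentence and one model term. Every subject with a change score already has a baseline CPA, so no subject is lost and no new data are needed.
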